8.3.5 Time Period and Frequency for Event Assessment and Follow-Up

For this study, all Grade 3 and 4 AEs, and all SAEs occurring from the time the first study product is initially given on Day 1 through the Day 29 visit will be documented, recorded, and reported.

8.3.5.1 Investigator Reporting of AEs

Information on AEs will be recorded on the appropriate CRF. All clearly related signs, symptoms, and results of diagnostic procedures performed because of an AE should be grouped together and recorded as a single diagnosis. If the AE is a laboratory abnormality that is part of a clinical condition or syndrome, it should be recorded as the syndrome or diagnosis rather than the individual laboratory abnormality. Each AE will also be described in terms of duration (start and stop date), severity, association with the study product, action(s) taken, and outcome.

8.3.6 Serious Adverse Event Reporting

8.3.6.1 Investigators Reporting of SAEs

Any AE that meets a protocol-defined criterion as an SAE that is judged to be related to either study product must be submitted within 24 hours of site awareness on an SAE form to the DMID Pharmacovigilance Group, at the following address:

DMID Pharmacovigilance Group
Clinical Research Operations and Management Support (CROMS)
[name]
[name]
SAE Hot Line: [name] (US) or [name] (outside US)
SAE [contact] (US) or [name] (outside US)
SAE Email Address: [contact]

Other supporting documentation of the event may be requested by the DMID Pharmacovigilance Group and should be provided as soon as possible. The DMID Medical Monitor will review and assess the SAE for regulatory reporting and potential impact on study subject safety and protocol conduct. At any time after completion of the study, if the site PI or appropriate sub-investigator becomes aware of an SAE that occurred during the subject's participation in the study, the site PI or appropriate sub-investigator will report the event to the DMID Pharmacovigilance Group.

SAEs that are judged to be not related to study product are still captured on the AE case report form, but do not require separate reporting to the DMID Pharmacovigilance Group.

8.3.6.2 Regulatory Reporting of SAEs

Following notification from the site PI or appropriate sub-investigator, DMID, as the IND Sponsor, will report any SUSAR in an IND safety report to the FDA and will notify all participating site PIs as soon as possible. DMID will report to the FDA any unexpected fatal or life-threatening suspected adverse reaction as soon as possible, but in no case later than 7 calendar days after the Sponsor's initial receipt of the information. If the event is not fatal or life-threatening, the IND safety report will be submitted within 15 calendar days after the Sponsor determines that the information qualifies for reporting as specified in 21 CFR Part 312.32. Relevant follow up information to an IND safety report will be submitted as soon as the information is available. Upon request from the FDA, DMID will submit to the FDA any additional data or information that the agency deems necessary, as soon as possible, but no case later than 15 calendar days after receiving the request.

SAEs that are not SUSARs will be reported to the FDA at least annually in a summary format which includes all SAEs.

Sites may have additional local reporting requirements (to the IRB and/or national regulatory authority).

8.3.7 Reporting of Pregnancy

8.4 Unanticipated Problems

8.4.1 Definition of Unanticipated Problems

An Unanticipated Problem (UP) is any event, incident, experience, or outcome that meets the following criteria:

- Unexpected in terms of nature, severity, or frequency given (a) the research procedures that are described in the protocol-related documents, such as the IRB-approved research protocol and informed consent document; and (b) the characteristics of the subject population being studied;
- Related to participation in the research (meaning there is a reasonable possibility that the incident, experience, or outcome may have been caused by the procedures involved in the research); and
- Suggests that the research places subjects or others at a greater risk of harm (including physical, psychological, economic, or social harm) than was previously known or recognized.

8.4.2 Unanticipated Problem Reporting

To satisfy the requirement for prompt reporting, all Ups will be reported using the following timeline:

- UPs that are SAEs will be reported to the IRB and to the Statistical and Data Coordinating Center (SDCC)/study Sponsor within 24 hours of the investigator becoming aware of the event per the above describe SAE reporting process.
- Any other UP will be reported to the IRB and to the SDCC/study Sponsor within 3 days of the investigator becoming aware of the problem.

9. STATISTICAL CONSIDERATIONS

9.1 Statistical Hypotheses

The primary hypothesis tests whether the time-to-recovery by Day 29 differs between the experimental and control arms.

Table 7. Hypothesis tests of interest for ACTT-3

| ACTT-3 | |
|--------------------|---|
| Primary hypothesis | RDV + interferon-beta-1a versus RDV + placebo |

Appendix C - ACTT-3: Remdesivir + Interferon Beta-1a

A key secondary hypothesis tests the null distribution of a similar distribution of 8-point ordinal scale at Day 15. For this, the parameter of interest is the “common odds ratio,” which quantifies the shift in the severity distribution resulting from treatment. For an efficacious treatment, an odds ratio greater than 1 quantifies an improvement in disease severity; a value of 2 indicates a bigger improvement than a value of 1.25. The null hypothesis to be tested is that the odds of improvement on the ordinal scale is the same for the control and experimental treatment arms (i.e., the common odds ratio is 1). It is worth noting that, for large sample sizes, the test based on the proportional odds model is nearly the same as the Wilcoxon rank sum test.

9.2 Sample Size Determination

Primary endpoint: The log-rank test will be used to compare treatment arms with respect to time to recovery. For the log-rank test, the two key determinants of power are the total number of events (i.e., recoveries) E and the treatment-to-control ratio of the rate of recovery, R . The number of events required for power $1 - \beta$ to detect a recovery rate ratio of θ using a two-tailed test at alpha=0.05 is approximately

$$E = \frac{4(1.96 + z_\beta)^2}{\{\ln(\theta)\}^2},$$

where z_β is the $100(1 - \beta)$ th percentile of the standard normal distribution.

The force of recovery (sometimes loosely referred to as the “recovery ratio”) is the analogue of the hazard ratio and the term “recovery rate ratio” is the analogue of the hazard ratio in this setting. A recovery rate ratio of 1.31 was reported in Cao, Wang, Wen et al. (2020) for a lopinavir/ritonavir trial that used time to improvement by 2 categories as primary endpoint. A preliminary review of data from ACTT-1 demonstrated a recovery rate ratio 1.312. It is unlikely the second component of treatment will have a similar effect size. Therefore a recovery ratio of 1.25 is assumed for this trial. A total of 723 recoveries are needed for a recovery ratio of 1.25 with 85% power. [Table 5](#) provides power for various recovery rate ratios.

Table 8. Number of recoveries needed for 85% power assuming a type I error rate of 5% for various recovery ratios.

| Recovery rate ratio (θ) | Number of recoveries needed for 85% power |
|-------------------------------------|---|
| 1.20 | 1080 |
| 1.25 | 723 |
| 1.30 | 523 |
| 1.35 | 400 |
| 1.40 | 318 |

Appendix C - ACTT-3: Remdesivir + Interferon Beta-1a

The study will enroll participants until 831 recoveries. Initially the study was powered for 723 recoveries in those in ordinal score 4-6 at baseline, with an increase to 831 recoveries due to anticipated lower efficacy in ordinal score 7. The same assumption will now be made that ordinal score 6 will have a lower efficacy, and therefore the number of recoveries will remain unchanged. However, we anticipate that approximately 90% of subjects recover within 28 days, and therefore the total sample size will be approximately 923. The date of study closure will be estimated based on enrollment rate and recovery/enrollment percentages.

Key secondary: A sample size can be computed using an (assumed) ordinal scale distribution for the control arm and the odds ratio representing clinical improvement. The odds ratio represents the odds of improvement in the ordinal scale for combination treatment relative to the control arm [Whitehead, 1993]. The sample size to detect a given odds ratio for 1:1 randomization using a 2-tailed test at level α is given by

$$\frac{12(z_{\alpha/2} + z_{\beta})^2}{\lambda^2(1 - \sum_{i=1}^K p_i^3)},$$

where λ is the log odds ratio, p_i is the overall probability (combined over both arms) of being in the i th category of the K ordinal outcomes, and $z_{\alpha/2}$ and z_{β} are the $1 - \alpha/2$ and $1 - \beta$ quantiles of the standard normal distribution.

[Table 6](#) displays five scenarios considered for outcome probabilities in the control arm for sample size determination. There is significant uncertainty with these assumptions given the limited data available. [Table 6](#) shows a range of sample sizes for odds ratios ranging from 1.25 to 2.5 for 85% power. For 90% power, increase the sample size by 17%. [Table 8](#) displays the probabilities of being in different categories of the ordinal scale under an odds ratio of 1.75. A total sample size of 396 gives approximately 85% power to detect an odds ratio of 1.75 using a 2-tailed test at level $\alpha = 0.05$. The categories of the 8-point ordinal scale are:

- Death;
- Hospitalized, on invasive mechanical ventilation or ECMO;
- Hospitalized, on non-invasive ventilation or high flow oxygen devices;
- Hospitalized, requiring supplemental oxygen;
- Hospitalized, not requiring supplemental oxygen – requiring ongoing medical care (COVID-19 related or otherwise);
- Hospitalized, not requiring supplemental oxygen – no longer requires ongoing medical care;
- Not hospitalized, but new or increased limitation on activities and/or requiring new or increased home oxygen;
- Not hospitalized, no limitations on activities.

Note that the data elements contributing to this scale will be captured separately, in order to facilitate different orderings or groupings, as might arise if external data provide information about the clinical course of disease.

Table 9: Possible scenarios for the distribution of ordinal outcomes for the control arm at Day 15.

| | Anticipated | Different scenarios for control arm | | | | |
|--|---|--|-------------|-------------|-------------|-------------|
| | | Scenario 1 | Scenario 2 | Scenario 3 | Scenario 4 | Scenario 5 |
| Severity Outcome | more mild disease \longleftrightarrow more severe disease | | | | | |
| | outcome (%) | outcome (%) | outcome (%) | outcome (%) | outcome (%) | outcome (%) |
| Death | 2 | 1 | 1 | 2 | 3 | |
| Hospitalized, on mechanical ventilation or ECMO | 1 | 1 | 1 | 1 | 3 | |
| Hospitalized, on non-invasive ventilation or high flow oxygen devices | 2 | 1 | 1 | 2 | 4 | |
| Hospitalized, requiring supplemental oxygen | 7 | 2 | 5 | 5 | 9 | |
| Hospitalized, not requiring supplemental oxygen – requiring ongoing medical care (COVID-19 related or otherwise) | 8 | 5 | 7 | 17 | 23 | |
| Hospitalized, not requiring supplemental oxygen – no longer requires ongoing medical care | 10 | 9 | 10 | 20 | 25 | |
| Not hospitalized, limitation on activities and/or requiring home oxygen | 30 | 36 | 35 | 25 | 18 | |
| Not hospitalized, no limitations on activities | 40 | 45 | 40 | 28 | 15 | |

Table 10: Sample size calculations for scenarios in Table 6 for a two-arm study assuming 85% power, a two-sided type I error rate of 5%, and various true odds ratios.

| True odds ratio | Total sample size | | | | |
|------------------------|--------------------------|------------|------------|------------|------------|
| | Scenario 1 | Scenario 2 | Scenario 3 | Scenario 4 | Scenario 5 |
| 1.25 | 2420 | 2554 | 2459 | 2293 | 2252 |
| 1.5 | 744 | 786 | 755 | 700 | 684 |
| 1.75 | 396 | 419 | 401 | 370 | 360 |
| 2.0 | 262 | 277 | 265 | 243 | 236 |
| 2.25 | 194 | 206 | 196 | 179 | 173 |

| True odds ratio | Total sample size | | | | |
|------------------------|--------------------------|------------|------------|------------|------------|
| | Scenario 1 | Scenario 2 | Scenario 3 | Scenario 4 | Scenario 5 |
| 2.5 | 154 | 163 | 155 | 141 | 136 |

Table 11. Treatment ordinal outcome proportions under an odds ratio of 1.75 for five scenarios in Table 5 at Day 15.

| Severity Outcome | Scenario 1 | Scenario 2 | Scenario 3 | Scenario 4 | Scenario 5 | |
|--|-------------|---|------------|------------|------------|------|
| | Anticipated | more mild disease ← → more severe disease | | | | |
| Death | 2 | 1.2 | 1 | 0.6 | 1 | 0.6 |
| Hospitalized, on mechanical ventilation or ECMO | 1 | 0.6 | 1 | 0.6 | 1 | 0.6 |
| Hospitalized, on non-invasive ventilation or high flow oxygen devices | 2 | 1.2 | 1 | 0.6 | 1 | 0.6 |
| Hospitalized, requiring supplemental oxygen | 7 | 4.3 | 2 | 1.2 | 5 | 3.0 |
| Hospitalized, not requiring supplemental oxygen – requiring ongoing medical care (COVID-19 related or otherwise) | 8 | 5.3 | 5 | 3.1 | 7 | 4.4 |
| Hospitalized, not requiring supplemental oxygen – no longer requires ongoing medical care; | 10 | 7.2 | 9 | 5.9 | 10 | 6.8 |
| Not hospitalized, limitation on activities and/or requiring home oxygen | 30 | 26.5 | 36 | 29.3 | 35 | 30.2 |
| Not hospitalized, no limitations on activities | 40 | 53.8 | 45 | 58.9 | 40 | 53.8 |

Note that columns may not sum to exactly 100 due to rounding errors.

Other key secondaries for testing combination therapy compared to control will be detailed in an addendum SAP

9.3 Populations for Analyses

An adjudication or review committee consisting of the DMID MO, her designees and the blinded statistical team may review endpoints, medications, deviations, and other special cases where expert opinion is requested for handling complicated cases.

The primary analysis will be based on an intention-to-treat population, including all subjects randomized. Similarly, safety analyses will be based a modified intent-to-treat population consisting of all subjects who received at least one dose of any investigational product.

9.4 Statistical Analyses

9.4.1 General Approach

This is a double-blind placebo controlled randomized trial testing a superiority hypothesis with a two-sided type I error rate of 5%. Secondary hypotheses have been ordered according to relative importance, with one key secondary hypothesis highlighted. These will be described according to the appropriate summary statistics (e.g., proportions for categorical data, means with 95% confidence intervals for continuous data, median for time-to-event data).

A statistical analysis plan will be developed and filed with the study sponsor prior to unblinding of study and database lock.

9.4.2 Analysis of the Primary Efficacy Endpoint

The primary efficacy analysis is a stratified log-rank test, where stratification is according to baseline disease severity as defined by ordinal scale. Deaths will be considered as never recovering and censored at Day 29. In ACTT-3, the analyses conducted will depend on the results from ACTT-1 according to [Table 4](#).

9.4.3 Analysis of the Secondary Endpoint(s)

The ordinal scale will be used to estimate a proportional odds model by disease strata. The hypothesis test will perform a stratified test to evaluate whether the common odds ratio for treatment is equal to one. The distribution of severity results will be summarized by treatment arm as percentages. Efforts to minimize loss-to-follow-up will be considerable. However, small amounts of missing data may occur. In such cases, subjects without final outcome data will be excluded from the analysis. Sensitivity analyses will evaluate the impact of making different assumptions about missing observations. These analyses will be defined in the SAP.

Differences in time-to-event endpoints (e.g., time to at least a one category improvement in ordinal scale) by treatment will be summarized with Kaplan-Meier curves and 95% confidence bounds. The same procedure will be used to compare time to at least a two-category improvement.

Change in ordinal scale at specific time points will be summarized by proportions (e.g., proportion who have a 1-, 2-, 3-, or 4-point improvement or 1-, 2-, 3-, 4-point worsening).

Binary data (e.g., incidence of new oxygen use) will be summarized as a percent with 95% confidence intervals. Comparisons between arms will be presented as differences in proportions with 95% confidence intervals.

Categorical data (e.g., 28-day mortality or ordinal scale by day) may be summarized according to proportions by category and/or odds ratios with confidence intervals.

Procedures for handling missing data, including informative censoring (e.g., a missing duration of oxygen use endpoint due to a death), will be described in the SAP.

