5.6.2 Retention

Retention of subjects is critical to the success of the trial since the primary endpoint is measured through Day 29 (+ 6-day window) and every effort should be made to retain subjects in the study. As such, after hospital discharge, subjects will be reminded of subsequent study visits and every effort will be made to accommodate the subject's schedule to facilitate follow-up within the specified visit window. However, there are many circumstances that impact a site's ability to obtain outcome information after discharge. For example, given the clinical course of COVID-19, a subject may be readmitted to another hospital after discharge and therefore be unavailable at Day 15 or Day 22. Even if a study visit is missed or study product is discontinued, every effort should be made to keep subjects in the study to monitor for safety, mortality and ordinal scale at Day 29. Subjects should not be withdrawn from the study because a site is unable to contact them for a follow-up visit.

Another common lost-to-follow-up scenario during ACTT-1, involved subjects (or their LARs) asking that the study products and blood draws be discontinued due to terminal illness. These subjects should also be encouraged to remain in study for the final Day 29 ordinal scale

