8.1.2.1 Measures of clinical support, limitations and infection control

The subject's clinical status, which is largely measured by the ordinal scale and NEWS, will be captured on each study day while hospitalized through Day 29 (+ 6-day window) or day after death whichever comes first. The ordinal scale will also be captured on the day after discharge from the hospital. This will be done so that discharge and death are accurately recorded and captured in the eClinical system. For subjects who received oxygen by nasal cannula or CPAP ventilatory support at night at home prior to having COVID-19, sites should assign a recovery ordinal scale score of 1 or 2 when discharged to home after recovery. The assignment of category 1 versus category 2 will depend on whether they have new or increased physical limitations post-COVID-19 and/or if they have new or increased home oxygen requirement compared with the pre-COVID-19 time period.

It is important to capture all deaths that occur during the study as this is one of the outcomes of the study. Death is a category on the ordinal scale. If a subject dies during the study, an ordinal scale assessment should be completed for the day after death because the ordinal scale captures the worst clinical assessment for the previous day. If a subject dies within the window of the final study visit (i.e., Day 29 + 6-day window), complete an ordinal scale assessment on the day after death.

If a subject is discharged prior to Day 15, clinical status is collected on Day 15 and 29 if the subject returns for an in-person clinic visit or by phone, home visit or remote telehealth procedure as per institutional standards if an in-person visit at the clinical trial site is not possible. Clinical status will also be captured on Day 22 during a phone call or remote telehealth visit. Unlike the NEWS, the ordinal scale can also be evaluated over the phone or by a remote telehealth procedure if the discharged subject is unable to return to the clinical trial site for visits on Day 15 and 29 as well as on Day 22.

Except for Day 1, when the ordinal scale and the NEWS is captured at the time of randomization, a site should try to complete the ordinal scale and the NEWS at approximately the same time each day. Ideally, complete the ordinal scale concurrently with NEWS just prior to study product administration, as time permits. The following measures are recorded for the ordinal scale:

- Hospitalization.
- Oxygen requirement.

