9.4.3 Analysis of the Secondary Endpoint(s)

- 1) The ordinal scale at Day 15 will be used to estimate a proportional odds model within different categories of the ordinal scale at baseline. The hypothesis test will perform a strata- adjusted test to evaluate whether the common odds ratio for treatment is equal to one. The distribution of severity results will be summarized by treatment arm as percentages. There will be efforts to minimize loss to follow-up. However, small amounts of missing data may occur. In such cases, outcomes may be imputed based on rules described in the SAP. Sensitivity analyses will evaluate the impact of making different assumptions about missing observations. These analyses will be defined in the SAP.
- 2) Differences in time-to-event endpoints (e.g., time to recovery or time to at least a one category improvement in ordinal scale, time to death) by treatment will be summarized with Kaplan-Meier curves and 95% confidence bounds, using the Fine-Gray approach for competing events when appropriate.
- 3) Analysis of mortality data will be evaluated using a Cox proportional hazards model.

4) Desirability of outcomes response (DOOR). A revised ordinal scale has been constructed to incorporate SAEs. SAE may be related or unrelated to study product. Any SAE occurring after study product administration through Day 15 (or through Day 29) will be counted:

| |
|---|
| 1- Recovered (OS 1,2,3) |
| 2- Improved by at least 1 OS from baseline & no SAE |
| 3- Improved by at least 1 OS from baseline & SAE |
| 4- No change in OS from baseline & no SAE |
| 5- No change in OS from baseline & SAE |
| 6- Worsened by at least 1 OS from baseline |
| 7- Death (OS 8) |

*OS = ordinal scale score based on the 8-point scale

This DOOR scale will be evaluated at Day 15 and Day 29, and between arm differences will be tested using a Mann-Whitney U-statistic.

5) Change from baseline in ordinal scale at specific time points will be summarized by proportions (e.g., proportion who have a 1-, 2-, 3-, or 4-point improvement or 1-, 2-, or 3-point worsening).

6) Duration of event (e.g., duration of mechanical ventilation) will be summarized according to median days with quartiles and mean with SD.

7) Binary data (e.g., incidence of new oxygen use) will be summarized as a percent with 95% confidence intervals. Comparisons between arms will be presented as differences in proportions with 95% confidence intervals.

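### ACTT-3's Day 15 ordinal key secondary is fixed as a complete-case analysis with no day named, although related scores are already collected; the likely bias is small, but the rule is cheap to replace

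*Protocol*

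**What the plan says.** Appendix C 9.1 makes the Day 15 distribution of the 8-point scale a key secondary hypothesis, with the common odds ratio as its parameter. Appendix C 9.4.3 specifies a proportional odds model and then turns to missing data: "However, small amounts of missing data may occur". The rule is: "In such cases, subjects without final outcome data will be excluded from the analysis". It adds: "Sensitivity analyses will evaluate the impact of making different assumptions about missing observations", and leaves the content of those analyses, and missing-data procedures generally, to the SAP.

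Appendix C 5.6.2 describes how outcomes come to be missing. One route is that "a subject may be readmitted to another hospital after discharge and therefore be unavailable at Day 15 or Day 22". The other is terminal illness: "Another common lost-to-follow-up scenario during ACTT-1, involved subjects (or their LARs) asking that the study products and blood draws be discontinued due to terminal illness".

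On data in hand, Appendix C 8.1.2.1 and 8.1.2.2 require a daily ordinal score in hospital and status at Days 15, 22 and 29 after discharge. In addition, "The ordinal scale will also be captured on the day after discharge from the hospital".

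For the same Day 15 endpoint in ACTT-4, the corresponding sentence of Appendix D 9.4.3 reads: "In such cases, outcomes may be imputed based on rules described in the SAP".

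**The concern.** Excluding subjects without an outcome means the odds ratio describes those whose status is known, not everyone randomized. That matters little if missingness is unrelated to outcome, but both routes named in Appendix C 5.6.2 point towards sicker subjects. If the arms lose such subjects at different rates, the estimate moves, in either direction.

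The rule also discards information. A subject discharged early, missed at Day 15 and reached at Day 22 has scores on both sides of the missing one, yet would be dropped if the final outcome means the Day 15 score.

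That reading is itself uncertain. Appendix C 5.6.2 and 7.2 use the word final for the Day 29 assessment. Read that way, the sentence could exclude a subject whose Day 15 score was observed. It needs repair on either reading.

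**Working it through.** **Inputs.** Appendix C 9.2, Table 9, Scenario 1 control distribution (death to no limitations): 2, 1, 2, 7, 8, 10, 30, 40%. Odds ratio 1.75, two-sided 5%, 85% power, stated N = 396; planned enrolment about 923. No ACTT-3 loss rate is given, so all loss patterns below are assumed.

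**Reproducing the plan's figure.** Dividing the control cumulative odds by 1.75 gives a treated distribution of 1.2, 0.6, 1.2, 4.3, 5.3, 7.2, 26.5, 53.8%, matching Table 11. With p̄ the mean of the two arms, Σp̄³ = 0.127. The protocol's formula gives

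N = 12 × (1.960 + 1.036)² / [0.5596² × (1 − 0.127)] = 107.7 / 0.2734 = 394.

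The stated 396 is reproduced closely, so the sample size is not in question.

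**Power.** With 0, 2, 5 and 8% of subjects excluded (8% is the loss assumed for ACTT-4 in Appendix D 9.2), power at N = 396 and odds ratio 1.75 is 85.2, 84.5, 83.3 and 82.2%. At N = 923 it stays above 99%. Lost power is not the issue.

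**Bias, same selection in both arms.** Remove the same fraction of each poor category from both arms and refit the proportional odds model to the expected proportions.

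- True odds ratio 1.00: it stays 1.00.
- True odds ratio 1.75, with 10% or 25% of categories 5–8 missing: 1.743 or 1.732, a change in the log odds ratio of −0.7% or −1.8%.
- True odds ratio 1.75, with 25% to 75% of categories 6–8 missing: 1.74 to 1.72.
- Loss confined to discharged subjects: less than 1% change in the log odds ratio.

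**Bias, unequal loss.** Losses are a percentage of each arm, spread over categories 5–8, which hold 12.0% of control and 7.2% of interferon subjects at odds ratio 1.75.

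| Control lost | Interferon lost | Share of that arm's categories 5–8 | Fitted OR (true 1.75) | Change in log OR |
|---|---|---|---|---|
| 2% | 1% | 17% / 14% | 1.725 | −2.6% |
| 2% | 0% | 17% / 0% | 1.66 | −9.4% |
| 5% | 2% | 42% / 28% | 1.65 | −10.5% |
| 1% | 2% | 8% / 28% | 1.84 | +9.2% |
| 1% | 3% | 8% / 41% | 1.92 | +16.5% |

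The effect is asymmetric: at odds ratio 1.75 the interferon arm has fewer poor outcomes, so one percentage point is a larger share of them.

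**Under the null, one-sided loss.** If only the interferon arm loses 2%, all from categories 6–8, a true 1.00 becomes 1.066 (1.06 if spread over categories 5–8). At N = 923 the test statistic shifts by ln(1.066) × √[923 × (1 − 0.0929)/12] = 0.0639 × 8.353 = 0.534. The two-sided type I error is Φ(0.534 − 1.96) + Φ(−0.534 − 1.96), about 8.3%.

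**The case against.** The case against has real weight.

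- **The protocol works to prevent this loss.** Remote visits still yield clinical status (Appendix C 1.1). Subjects who stop study drug stay in follow-up to Day 29 (7.1.1). Investigators are discouraged from withdrawing subjects for missed visits (5.6.2, 7.2). Terminally ill subjects are encouraged to stay for a Day 29 score by chart review or phone.
- **Deaths are not missing.** A recorded death is category 8.
- **The terminal-illness remark is about ACTT-1**, and what was requested was stopping products and blood draws. ACTT-3 no longer enrols categories 6 and 7, so it may be rarer here.
- **Unequal loss is an assumption.** The injection is blinded (6.3.2) and nothing in the document suggests the arms differ. Several rows of the table need a large share of one arm's poor outcomes to vanish.
- **The SAP is to cover missing data**, and sensitivity analyses are promised.

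The first four points limit the size of the problem, and all stand. The fifth stands only in part. The exclusion rule is fixed in the protocol, so an SAP that imputed in the main analysis would contradict it, and sensitivity analyses leave the headline estimate unchanged. The retention effort for terminal subjects aims at Day 29, whereas this endpoint is Day 15.

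A reader might go further and infer that the odds ratio is materially biased, or that harm from interferon is being hidden, given that category 6 enrolment closed on a DSMB risk concern. The documents do not support that: they give no loss rate and no sign of a difference between arms.

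**Conclusion.** The point holds as a weakness in a rule that the protocol itself fixes. The main Day 15 analysis is complete-case, the day is not named, the protocol's own account of loss includes outcome-related routes, and data that could inform the missing scores are already collected. Appendix D permits imputation for the same endpoint.

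The bias is probably small. It is nil under the null when selection depends on outcome alone and is equal between arms. At odds ratio 1.75 it is under 2% of the log odds ratio when up to a quarter of categories 5–8 is missing equally. It approaches or passes 10% only with unequal loss, typically 2 to 3 percentage points, or one point if interferon loses more. These sizes rest on Table 9 Scenario 1, a true odds ratio of 1.75 and assumed loss patterns. Nor is this a breach of intention-to-treat as written, because Appendix C 9.3 states that principle for the primary analysis.

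**What to change.** In Appendix C 9.4.3, replace the exclusion sentence with a rule to this effect: all randomized subjects are included in the Day 15 analysis; a death known to have occurred by Day 15 is category 8; other missing Day 15 scores are imputed, for example by multiple imputation, from baseline stratum, recorded daily scores and any Day 22 or Day 29 status. Keep complete-case as a sensitivity analysis, and add one that scores withdrawals for terminal illness as category 8.

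Simple carry-forward of the last in-hospital score is not recommended as the main rule, because a terminal subject last seen in category 5 who probably died would be recorded as category 5.

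The cost is one protocol sentence and an imputation specification, with no new data or patients. The downside is that a few Day 15 scores rest on an imputation model instead of observation.
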